## 10.7. Appendix 7: ECG Findings of Potential Clinical Concern

ECG Findings That May Qualify as AEs

• Marked sinus bradycardia (rate <40 bpm) lasting minutes.

• New PR interval prolongation >280 msec.

• New prolongation of QTcF to >480 msec (absolute) or by <math>\geq 60</math> msec from baseline.

• New-onset atrial flutter or fibrillation, with controlled ventricular response rate: ie, rate <120 bpm.

• New-onset type I second-degree (Wenckebach) AV block of >30 seconds' duration.

• Frequent PVCs, triplets, or short intervals (<30 seconds) of consecutive ventricular complexes.

ECG Findings That May Qualify as SAEs

• QTcF prolongation >500 msec.

• New ST-T changes suggestive of myocardial ischemia.

• New-onset left bundle branch block (QRS >120 msec).

• New-onset right bundle branch block (QRS >120 msec).

• Symptomatic bradycardia.

• Asystole:

• In awake, symptom-free patients in sinus rhythm, with documented periods of asystole <math>\geq 3.0</math> seconds or any escape rate <40 bpm, or with an escape rhythm that is below the AV node;

• In awake, symptom-free patients with atrial fibrillation and bradycardia with 1 or more pauses of at least 5 seconds or longer;

• Atrial flutter or fibrillation, with rapid ventricular response rate: rapid = rate >120 bpm.

• Sustained supraventricular tachycardia (rate >120 bpm) ("sustained" = short duration with relevant symptoms or lasting >1 minute).

- Ventricular rhythms >30 seconds' duration, including idioventricular rhythm (heart rate <40 bpm), accelerated idioventricular rhythm (HR 40 bpm to <100 bpm), and monomorphic/polymorphic ventricular tachycardia (HR >100 bpm (such as torsades de pointes)).
- Type II second-degree (Mobitz II) AV block.
- Complete (third-degree) heart block.

#### **ECG Findings That Qualify as SAEs**

- Change in pattern suggestive of new myocardial infarction.
- Sustained ventricular tachyarrhythmias (>30 seconds' duration).
- Second- or third-degree AV block requiring pacemaker placement.
- Asystolic pauses requiring pacemaker placement.
- Atrial flutter or fibrillation with rapid ventricular response requiring cardioversion.
- Ventricular fibrillation/flutter.
- At the discretion of the investigator, any arrhythmia classified as an adverse experience.

The enumerated list of major events of potential clinical concern are recommended as "alerts" or notifications from the core ECG laboratory to the investigator and Pfizer study team, and not to be considered as all inclusive of what to be reported as AEs/SAEs.

### 10.8. Appendix 8: Prohibited Concomitant Medications That May Result in DDI

The prohibited concomitant medications listed below should not be taken with PF-07081532 for the period of time at least equal to the required washout period listed in the table, and throughout the conduct of the study.

The Pfizer study team is to be notified of any prohibited medications taken during the study. After consulting with the sponsor, the investigator will make a judgement on the ongoing participation of any participant with prohibited medication use during the study.

This list of drugs prohibited for potential DDI concerns with the IMP may be revised during the course of the study with written notification from sponsor, to include or exclude specific drugs or drug categories for various reasons (eg, emerging DDI results for the IMP, availability of new information in literature on the DDI potential of other drugs).

This is not an all-inclusive list. Site staff should consult with the sponsor or designee with any questions regarding potential DDI.

Drug Category	Drugs (Therapeutic Class)	Washout Period Requirement Prior to the First Dose of Study Intervention
CYP3A Inhibitor (strong)	Boceprevir (Antiviral), Ceritinib (Kinase Inhibitor), Clarithromycin (Antibiotic), Cobicistat (Pharmacokinetic Enhancer), Conivaptan (Diuretic), Danoprevir and Ritonavir (Antiviral), Elvitegravir and Ritonavir (Treatment of AIDS), Grapefruit juice (Food Product), Idelalisib (Kinase Inhibitor), Indinavir (Protease Inhibitor), Indinavir and Ritonavir (Protease Inhibitor), Itraconazole (Antifungal), Ketoconazole (Antifungal), LCL161 (Cancer Treatment), Lopinavir and Ritonavir (Protease Inhibitor), Mibefradil (Calcium Channel Blocker), Mifepristone (Antiprogesterin), Nefazodone (Antidepressant), Nelfinavir (Protease Inhibitor), Posaconazole (Antifungal), Ribociclib (Kinase Inhibitor), Ritonavir (Protease Inhibitor), Saquinavir (Protease Inhibitor), Saquinavir and Ritonavir (Protease Inhibitor), Telaprevir (Antiviral), Telithromycin (Antibiotic),	5 half-lives plus 14 days

Drug Category	Drugs (Therapeutic Class)	Washout Period Requirement Prior to the First Dose of Study Intervention
	Tipranavir and Ritonavir (Protease Inhibitor), Troleandomycin (Antibiotic), Tucatinib (Kinase Inhibitor), Viekira Pak (Antiviral), Voriconazole (Antifungal)	
CYP3A Inducer (strong)	Apalutamide (Antiandrogen), Avasimibe (Antilipemic), Carbamazepine (Anticonvulsant), Enzalutamide (Antiandrogen), Ivosidenib (Cancer Treatment), Lumacaftor (Cystic Fibrosis Treatment), Mitotane (Antineoplastic), Phenobarbital (Anticonvulsant), Phenytoin (Anticonvulsant), Rifampin (Antibiotic), Rifapentine (Antibiotic), St. John's wort extract (Herbal Medication)	5 half-lives plus 14 days
OATP (1B1/1B3) Inhibitor	Atazanavir and Ritonavir (Protease Inhibitor), Clarithromycin (Antibiotic), Cyclosporine (Immunosuppressant), Erythromycin (Antibiotic), Gemfibrozil (Fibric Acid Derivative), Lopinavir and Ritonavir (Protease Inhibitor), Rifampin (Antibiotic), Simeprevir (Antiviral)	2 weeks or 5 half-lives, whichever is longer
CYP2C19 Substrate	BMS-823778 (Diabetes Treatment), Clobazam (Benzodiazepine), Clopidogrel (Antiplatelet), Diazepam (Benzodiazepine), Gliclazide (Sulfonylurea), Hexobarbital (Hypnotic – Sedative), Lansoprazole (Proton Pump Inhibitor), Mephobarbital (Anticonvulsant), Omeprazole (Proton Pump Inhibitor), Pantoprazole (Proton Pump Inhibitor), Proguanil (Antimalarial), Rabeprazole (Proton Pump Inhibitor), S-mephenytoin (Anticonvulsant), Tilidine (Treatment of Pain & Inflammation), Voriconazole (Antifungal)	2 weeks or 5 half-lives, whichever is longer

Investigators should consult the SRSD for active comparator for information regarding medication that is prohibited for concomitant use.

Investigators should consult the product label for any other medication used during the study for information regarding medication that is prohibited for concomitant use.

### 10.9. Appendix 9: Prohibited Medications Not Permitted From Screening

Drug class/Name	Duration Not Permitted from Screening
TZDs: eg, pioglitazone; rosiglitazone Subcutaneously administered agents for glycemic control: eg, insulin, exenatide, liraglutide, pramlintide	Within 3 Months of Screening
Other oral anti-diabetic medications: 
 
• Sulfonylureas: eg, acetohexamide, chlorpropamide, tolazamide, tolbutamine;
 
• Glimepiride, glipizide, glyburide;
 
• Meglitinide analogues, eg, repaglinide, nateglinide;
 
• DPP-4i eg, sitagliptin, saxagliptin;
 
• Vildagliptin;
 
• <math>\alpha</math>-glucosidase inhibitors, eg, acarbose, miglitol;
 
• SGLT2 inhibitors, eg, canagliflozin.
 
	Within 4 Weeks of Screening
Systemic glucocorticoids, eg, prednisone, dexamethasone, triamcinolone, budesonide, betamethasone. Note: As an exception, steroid-containing inhalers, nasal sprays, and topical formulations are permitted.	
Immunosuppressants, eg, cyclosporine and tacrolimus.	
Appetite- or weight-modifying medications, including non-prescription or herbals.	
Pharmacological agents with approved indication for weight loss, eg, orlistat and sibutramine.	
(Medical-grade) marijuana, regardless of medical indication.	
Anti-psychotic medications, eg olanzapine, risperidone.	
Antidepressant medications, eg tricyclic agents, selective serotonin reuptake inhibitors, and serotonin/norepinephrine reuptake inhibitors.	
Coumarin-type anticoagulants or other anticoagulants (eg, dabigatran).	
Anticonvulsants, if prescribed for a seizure disorder.	
Opioids.	
Antiarrhythmics.	
Non-selective $\beta$ -blockers.	
Thiazide diuretics >25 mg per day.	
Sympathomimetic agents.	

## 10.10. Appendix 10: Abbreviations

The following is a list of abbreviations that may be used in the protocol.

Abbreviation	Term
%CV	percent coefficient of variation
Abs	absolute
ADL	activities of daily living
AE	adverse event
ALT	alanine aminotransferase
AST	aspartate aminotransferase
AUC	area under the concentration-time curve
AUC inf	area under the concentration-time curve from time 0 to infinity
AUC last	area under the concentration-time profile from time 0 to the time of the last quantifiable concentration
AUC (0-4)	area under the curve from 0 to 4 hours
AUC 24	area under the concentration-time curve over 24 hours
AUC inf	area under the concentration-time curve to infinity
AV	atrioventricular
BBS	Biospecimen Banking System
BCRP	Breast Cancer Resistance Protein
BMI	body mass index
BP	blood pressure
Bpm	beats per minute
BUN	blood urea nitrogen
cAMP	3'-5'-cyclic adenosine monophosphate
CFB	change from baseline
CFR	Code of Federal Regulations
CI	confidence interval
CIOMS	Council for International Organizations of Medical Sciences
CK	creatinine kinase
CL	clearance
CL/F	apparent clearance
CL p	plasma clearance
C av	average concentration
C min	minimum observed concentration
C max	maximum observed concentration
CO 2	carbon dioxide (bicarbonate)
CONSORT	Consolidated Standards of Reporting Trials
COVID-19	coronavirus disease 2019
CRF	case report form
CRO	contract research organization
CRU	clinical research unit
CSR	Clinical Study Report
CT	clinical trial

Abbreviation	Term
CV	co-efficient of variation
CYP	cytochrome P450
DCT	data collection tool
DDI	drug-drug interaction
DILI	drug-induced liver injury
DMC	Data Monitoring Committee
DPP-4i	dipeptidyl peptidase-4 inhibitors
DU	dispensable unit
EC	ethics committee
ECC	emergency contact card
ECG	electrocardiogram
eCRF	electronic case report form
EDB	exposure during breastfeeding
EDP	exposure during pregnancy
EDR	extemporaneous dispensing record
eGFR	estimated glomerular filtration rate
EMA	European Medicines Agency
EU	European Union
EudraCT	European Clinical Trials Database
FPG	fasting plasma glucose
FPI	fasting plasma insulin
FSBG	fingerstick blood glucose
FSH	follicle-stimulating hormone
FU	follow-up
GCP	Good Clinical Practice
GFR	glomerular filtration rate
GGT	gamma-glutamyl transferase
GI	gastrointestinal
GLP-1	glucagon-like peptide-1
GLP-1R	glucagon-like peptide-1 receptor
H	hour
HbA1c	Glycated hemoglobin
HBcAb	hepatitis B core antibody
HBsAb	hepatitis B surface antibody
HBsAg	hepatitis B surface antigen
HCVAb	hepatitis C antibody
HDL	high density lipoprotein
HIV	human immunodeficiency virus
HOMA-IR	homeostatic model assessment of insulin resistance
HR	heart rate
HRT	hormone replacement therapy
IB	Investigator's Brochure
ICD	informed consent document

Abbreviation	Term
ICH	International Council for Harmonisation of Technical Requirements for Pharmaceuticals for Human Use
ID	identification
IND	Investigational New Drug
INR	international normalized ratio
IP	investigational product
IPAL	Investigational Product Accountability Log
IRB	Institutional Review Board
IRT	Interactive Response Technology
IV	intravenous(ly)
IVGTT	intravenous glucose tolerance test
K 2 EDTA	dipotassium ethylenediaminetetraacetic acid
k el	terminal phase rate constant
kg	kilogram
K i	mean binding inhibition constant
LBBB	left bundle branch block
LDL	low density lipoprotein
LFT	liver function test
Log e	natural logarithm with the base e
MATE	multi-drug and toxin extrusion protein
MCH	mean corpuscular hemoglobin
MCHC	mean corpuscular hemoglobin concentration
MCV	mean corpuscular volume
MDG	mean daily glucose
MEN2	multiple endocrine neoplasia syndrome type 2
mg/dL	milligram(s) per deciliter
μmol/L	micromole per liter
MDRD	modification of diet in renal disease
min	minute; minimum
MMTT	mixed meal tolerance test
msec	millisecond
MTC	medullary thyroid cancer
MTD	maximum tolerated dose
MDR1	multidrug resistance protein 1
N/A	Not applicable
N	total number
NC	not calculated
NHP	non-human primate
nM	nanomolar
NOAEL	no observed adverse effect level
NSAID	non-steroidal anti-inflammatory drug
OAT	organic anion transporter
OATP	organic anion transporting polypeptide

Abbreviation	Term
OCT	organic cation transporter
PD	pharmacodynamic(s)
P-gp	P-glycoprotein
PI	Principal Investigator
PK	pharmacokinetic(s)
PT	prothrombin time
PTR	peak-to-trough ratio
PVC	premature ventricular contraction
QD	once daily
QT	duration of ventricular depolarization and subsequent repolarization. Duration resides between beginning of QRS complex to end of the T wave
QTc	corrected QT
QTcF	QTc corrected using Fridericia's formula
qual	qualitative
R ac	accumulation ratio based on AUC (observed)
R ac,Cmax	C max accumulation ratio
RBC	red blood cell
SAE	serious adverse event
SAP	Statistical Analysis Plan
SCr	serum creatinine
SD	standard deviation
SGLT2	sodium-glucose cotransporter-2
SoA	schedule of activities
SOP	standard operating procedure
SRSD	single reference safety document
SS	steady state
SSID	single subject identifier
SToD	Study Team on Demand
SUSAR	Suspected Unexpected Serious Adverse Reaction
t 1/2	terminal phase half life
T2DM	type 2 diabetes mellitus
T4	free thyroxine
TBD	to be determined
TBA	total bile acids
TBili	total bilirubin
TEAE	treatment-emergent adverse event
THC	tetrahydrocannabinol
T max	time to reach C max
TSH	thyroid stimulating hormone
TZD	thiazolidinedione
UGT	uridine 5'-diphospho-glucuronosyltransferase
ULN	upper limit of normal

Abbreviation	Term
US	United States
$V_{ss}$	steady-state volumes of distribution
$V_z/F$	apparent volume of distribution for extravascular dosing
WBC	white blood cell
WOCBP	woman/women of childbearing potential
WONCBP	woman/women of non-childbearing potential

1. VERSION HISTORY

Table 1. Summary of Changes

Version/ Date	Associated Protocol Amendment	Rationale	Specific Changes
1 14 th Jan 2022	N/A	
 Original protocol 	N/A
2 28 th Jul 2022	N/A	
 Based on data review before database release, SQE (#PR2205605) was opened regarding confirmed aberrant glucose values reported by the site. SAP amendment is supported by DMB02 SOP and QMS-01 SOP Repeated wording for summarization of change from baseline on safety laboratories Listings of laboratory parameter of interest should only be listed/ Alignment with C3991002 outputs using Pfizer standards for reporting Physical examination data is not collected in this study 	
Impacted sections of SAP V1:
 
Section 3.3.1: reference to glucose AUC₀₋₄ removed
 
Section 3.3.4 - Change from baseline in MDG - removed
 
Section 5.3.5: reference to glucose AUC₀₋₄ and AUC₂₄ removed
 
Section 6.3.1: reference to glucose AUC₀₋₄ removed
 
Section 6.3.4: entire section removed
 
Section 3.4.1.2 removed
 
Section 6.7.1: Focused Laboratory Summaries on Endpoints of Interest removed
 
Section 6.7.2: Entire section removed

2. INTRODUCTION

This statistical analysis plan amendment (SAP) provides the detailed methodology for summary and statistical analyses of the data collected in Study C3991003 issued on September, 21st 2021.

2.1. Modifications to the Analysis Plan Described in the Protocol

The following endpoints

- *The MDG will be computed by $AUC_{24/24}$ hour.*
- *The $AUC_{(0-4)}$ for glucose will also be calculated.*

as described in Section 9.3.4 of the protocol has been removed due to aberrant glucose values (see [Version History](#)).

2.2. Study Objectives, Endpoints, and Estimands

Objectives	Endpoints
Primary:	Primary:

 • To evaluate the safety and tolerability of multiple doses of PF-07081532, administered orally, in adult participants with inadequately controlled T2DM on metformin and if enrolled, in non-diabetic participants with obesity. 	
 • Assessment of AEs, safety laboratory tests, vital signs and 12-lead ECGs.
Secondary:	Secondary:

 • To characterize plasma PK of PF-07081532 following multiple doses administered orally, in adult participants with inadequately controlled T2DM on metformin and if enrolled, in non-diabetic participants with obesity. 	
 • PF-07081532 plasma PK parameters AUC_{24}, C_{max}, T_{max} on Day 1 and Day 42 and $t_{1/2}$ on Day 42, as data permit.
Tertiary/Exploratory:	Tertiary/Exploratory:

 • To characterize the PD effect on glucose, insulin, glucagon, and C-peptide excursions after a MMTT following multiple doses of PF-07081532, administered orally, in adult participants with inadequately controlled T2DM on metformin. 	
 • CFB in response to MMTT at all postdose timepoints as specified in the SoA for $AUC_{(0-4)}$ for glucose, insulin, glucagon, and C-peptide.

 • To explore the PD effect on MDG*, HbA1c*, plasma glucose, plasma insulin, and HOMA-IR following multiple doses of PF-07081532, administered orally, in adult participants with T2DM inadequately controlled on metformin and, if enrolled, in non-diabetic participants with obesity. 	
 • CFB at all post-dose timepoints as specified in the SoA for: 
 ○ Fasting plasma glucose; ○ Fasting plasma insulin; ○ HOMA-IR; ○ HbA1c*; ○ MDG*.

Objectives	Endpoints

 To assess the PD effect on body weight changes following multiple doses of PF-07081532, administered orally, in adult participants with T2DM inadequately controlled on metformin and if enrolled, in non-diabetic participants with obesity. 	
 CFB in body weight at all post-dose timepoints as specified in the SoA.

 To further characterize plasma PK of PF-07081532 following multiple doses administered orally, in adult participants with inadequately controlled T2DM on metformin and if enrolled, in non-diabetic participants with obesity. 	
 Additional PF-07081532 plasma PK parameters following multiple dose administration including, as data permit: AUC_{24(dn)}, AUC_{inf}, AUC_{last}, C_{av}, CL/F, C_{max(dn)}, C_{min}, R_{ac}, R_{ac,Cmax}, PTR, V_{Z/F}

* not analyzed in non-diabetic population with obesity, if enrolled

2.2.1. Primary Estimand(s)

Not applicable because C3991003 is a Phase 1 study with no estimands on safety endpoints

2.2.2. Secondary Estimand(s)

Not applicable because C3991003 is a Phase 1 study with no estimands on PK parameters

2.2.3. Additional Estimand(s)

Not applicable because C3991003 is a Phase 1 study with no estimands on exploratory or tertiary endpoints

2.3. Study Design

The purpose of this study is to evaluate the safety, tolerability, and PK of multiple doses of PF-07081532 in participants with T2DM, inadequately controlled on metformin. The study may also enroll non-diabetic participants with obesity.

The study will also assess the effect on PD biomarkers, including MDG.

[figure not shown]
This is a randomized, double-blind (investigator- and participant- blind), sponsor-open, placebo-controlled, multiple oral dose-escalating study of PF-07081532.

In this study, adult participants with T2DM inadequately controlled on metformin will be enrolled and will receive PF-07081532 or placebo daily, for 42 days.

- Enrollment in 3 cohorts is planned with approximately 12 participants (9 PF-07081532: 3 placebo) per cohort.

A sample dosing scheme is provided below. Dosing in Cohort 1 will be conducted as shown. Increments in doses and duration of dosing at each step for subsequent cohorts, as well as the number of cohorts conducted, may be adjusted based on emerging data. The dosing scheme for each cohort will be provided in writing prior to its initiation.

Figure 1. Dose Titration Scheme

If a participant does not tolerate dose increment to the next dose level, as determined by the investigator and with notification to the sponsor, the participant may be reverted to the previously tolerated dose level. Following this dose modification, 2 separate attempts at increasing the dose to the next dose level are permitted, per investigator discretion. If, per investigator assessment, unacceptable intolerance (eg, severe vomiting) occurs shortly following dose administration, the dose will not be re-administered on the same day, and the participant may resume dosing at the current dose level at the next scheduled dosing time. Participants whose dose level is tolerability-limited may continue in the study for the intended duration of their assigned cohort at their own individual MTD, as judged to be appropriate by the PI and sponsor.

The planned cohorts in the study (Cohorts 1-3) may be conducted concurrently, partially overlapping or sequentially. The sponsor may decide not to conduct all planned cohorts, if it is judged that study objectives have been met. Up to 3 additional cohorts may be enrolled if judged necessary to meet the study objectives. One or more of the study cohorts may be conducted in non-diabetic participants with obesity.

3. ENDPOINTS AND BASELINE VARIABLES: DEFINITIONS AND CONVENTIONS

Baseline is defined as the assessments performed on Day -1 for all endpoints, unless otherwise specified.

3.1. Primary Endpoint(s)

The safety endpoints which will be measured during the study constitute the primary endpoints. Where applicable, details of the endpoints to be derived and definition of baseline are also provided.

The following data are considered in standard safety summaries (see protocol for collection days and list of parameters):

- *Adverse events;*
- *Laboratory data;*
- *Vital signs data;*
- *ECG results.*

3.1.1. Adverse Events

An adverse event is considered treatment emergent (TEAE) relative to a given treatment if:

- the event starts during the effective duration of treatment (i.e. starting after or on the first dose but before the last dose plus lag time)

The effective duration of treatment is determined by the lag time. Any event occurring within the lag time, whether this occurs during a break in treatment or at the end of treatment, is attributed to the corresponding treatment period. The lag time is defined by the Pfizer Standard of 365 days post last dose of IP.

Adverse events occurring up to the first dose of active treatment on Day 1 will be considered non-treatment emergent.

A 3-tier approach for summarizing AEs will not be used for this study as there is a low number of subjects planned to be enrolled per treatment group, although risk differences and related summaries for AEs of interest will be presented as defined in 3.4.1.1.

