**Figure 1. Sample Dosing Scheme**

If a participant does not tolerate dose increment to the next dose level, as determined by the investigator and with notification to the sponsor, the participant may be reverted to the previously tolerated dose level. Following this dose modification, 2 separate attempts at increasing the dose to the next dose level are permitted, per investigator discretion. If, per investigator assessment, unacceptable intolerance (eg, severe vomiting) occurs shortly following dose administration, the dose will not be re-administered on the same day, and the participant may resume dosing at the current dose level at the next scheduled dosing time. Participants whose dose level is tolerability-limited may continue in the study for the intended duration of their assigned cohort at their own individual MTD, as judged to be appropriate by the PI and sponsor.

The planned cohorts in the study (Cohorts 1-3) may be conducted concurrently, partially overlapping or sequentially. The sponsor may decide not to conduct all planned cohorts, if it is judged that study objectives have been met. Up to 3 additional cohorts may be enrolled if judged necessary to meet the study objectives. One or more of the study cohorts may be conducted in non-diabetic participants with obesity, see [Section 4.2.1](#) and [Section 5](#).

Determination of eligibility will occur within 28 days of randomization based on criteria including medical history, vital sign, ECG and laboratory parameters, as detailed in [Section 5](#). Participants deemed eligible will be admitted to the CRU 7 days prior to start of dosing (Day -7) and will remain on-site until at least Day 45, post first dose.

The treatment period with double-blind study intervention will be 42 days, with study drug administered once daily. The participants within a given cohort will be blinded to the study treatment (PF-07081532 versus placebo). Participants who discontinue prior to completion of the study may be replaced, at the discretion of the PI and sponsor.

Upon discharge from the CRU, participants will return to the CRU 7 to 14 days after the last administration of IP for an on-site follow-up visit. A further follow-up contact with participants will be conducted at least 28 days and up to 35 days after the last administration of IP; this contact may be done via a phone call.

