#### **8.3.1. Time Period and Frequency for Collecting AE and SAE Information**

The time period for actively eliciting and collecting AEs and SAEs (“active collection period”) for each participant begins from the time the participant provides informed consent, which is obtained before the participant’s participation in the study (ie, before undergoing any study-related procedure and/or receiving study intervention), through and including a minimum of 28 calendar days after the last administration of the study intervention.

Follow-up by the investigator continues throughout and after the active collection period and until the AE or SAE or its sequelae resolve or stabilize at a level acceptable to the investigator.

For participants who are screen failures, the active collection period ends when screen failure status is determined.

If the participant withdraws from the study and also withdraws consent for the collection of future information, the active collection period ends when consent is withdrawn.

If a participant permanently discontinues or temporarily discontinues study intervention because of an AE or SAE, the AE or SAE must be recorded on the CRF and the SAE reported using the CT SAE Report Form.

Investigators are not obligated to actively seek information on AEs or SAEs after the participant has concluded study participation. However, if the investigator learns of any SAE, including a death, at any time after a participant has completed the study, and he/she considers the event to be reasonably related to the study intervention, the investigator must promptly report the SAE to Pfizer using the CT SAE Report Form.

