### 10.3. Appendix 3: Adverse Events: Definitions and Procedures for Recording, Evaluating, Follow-Up, and Reporting

#### 10.3.1. Definition of AE

AE Definition

• An AE is any untoward medical occurrence in a patient or clinical study participant, temporally associated with the use of study intervention, whether or not considered related to the study intervention.

• Note: An AE can therefore be any unfavorable and unintended sign (including an abnormal laboratory finding), symptom, or disease (new or exacerbated) temporally associated with the use of study intervention.

Events Meeting the AE Definition

• Any abnormal laboratory test results (hematology, clinical chemistry, or urinalysis) or other safety assessments (eg, ECG, radiological scans, vital sign measurements), including those that worsen from baseline, considered clinically significant in the medical and scientific judgment of the investigator. Any abnormal laboratory test results that meet any of the conditions below must be recorded as an AE:

• Is associated with accompanying symptoms.

• Requires additional diagnostic testing or medical/surgical intervention.

• Leads to a change in study dosing (outside of any protocol-specified dose adjustments) or discontinuation from the study, significant additional concomitant drug treatment, or other therapy.

• Exacerbation of a chronic or intermittent preexisting condition, including either an increase in frequency and/or intensity of the condition.

• New condition detected or diagnosed after study intervention administration, even though it may have been present before the start of the study.

• Signs, symptoms, or the clinical sequelae of a suspected drug-drug interaction.

• Signs, symptoms, or the clinical sequelae of a suspected overdose of either study intervention or a concomitant medication. Overdose per se will not be reported as an AE or SAE unless it is an intentional overdose taken with possible suicidal/self-harming intent. Such overdoses should be reported regardless of sequelae.

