6.2.1.3. Adverse Events

Adverse events will be reported in accordance with the sponsor reporting standards.

Incidence and severity of treatment emergent adverse event (TEAE) tables will additionally be produced ('All causality' and 'Treatment related', separately) to summarise the total number of adverse events by preferred term, which will be reported by treatment group and overall.

A set of individual profile plots will be produced separately for each TEAE of interest. Each plot will include horizontal bars by participant which will represent if/when a participant experienced the TEAE of interest (measured in days). The x-axis will represent time and the bars will be colored by severity, with the plots paged by treatment group. Multiple events for the same participant of the same TEAE would therefore be represented by multiple horizontal bars.

Time to the first occurrence of TEAEs of interest will be produced using Cumulative Incidence Plots as described in [Section 5.2.6](#). Participants who discontinue from the study, discontinue from IP will be censored at the discontinuation/initiation date.

A separate plot for each TEAE will be produced separately.

The above will also be produced separately for the time to the first recurrence of the TEAEs of interest. There will be a separate line for each treatment group.

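### The SAP's treatment-emergent rule has no limb for an adverse event already ongoing at first dose that then worsens

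*SAP*

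**What the plan says.** SAP 3.1.1 gives one criterion for treatment emergence, and it is a date criterion: "the event starts during the effective duration of treatment", which it explains as an onset no earlier than the first dose and ahead of the last dose plus a lag. A further sentence settles the status of earlier events without exception: "Adverse events occurring up to the first dose of active treatment on Day 1 will be considered non-treatment emergent". No other SAP section mentions an increase in severity relative to the pre-dose state.

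Pre-dose AEs will be on record. Under protocol 8.3.1 the collection period "begins from the time the participant provides informed consent". Protocol 4.1 adds a confined period before dosing: "Participants deemed eligible will be admitted to the CRU 7 days prior to start of dosing (Day -7").

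Protocol 10.3.1 lists among the events that meet the AE definition: "Exacerbation of a chronic or intermittent preexisting condition, including either an increase in frequency and/or intensity of the condition".

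The treatment-emergent flag drives the main tolerability outputs. SAP 6.2.1.3 states: "Incidence and severity of treatment emergent adverse event (TEAE) tables will additionally be produced", and also "A set of individual profile plots will be produced separately for each TEAE of interest". It adds cumulative-incidence plots of first occurrence and first recurrence. SAP 3.4.1.1 names the events of interest as nausea, vomiting and diarrhoea, and SAP 3.1.1 promises risk differences for them.

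**The concern.** AEs are part of the primary endpoint. Protocol 4.2 explains that the study compares starting doses and titration steps because of gastrointestinal tolerability. A participant with mild nausea before Day 1 whose nausea becomes moderate or severe on study intervention is informative for that purpose. A rule based on start date alone cannot register the change if the event stays on its original record.

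The other primary safety data are treated differently. SAP 3.1.2 to 3.1.4 assess laboratory values, vital signs and ECGs against each participant's Day -1 value. Only the AE rule has no way to express deterioration from a pre-dose state.

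At stake are the incidence and severity figures for the three gastrointestinal terms in groups of nine, where one participant is a visible share.

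**Working it through.** The documents state no figure that depends on this rule, and protocol 9.5 says the sample size was chosen empirically, so there is no plan figure to reproduce. The check is a reading of the rule against each possible case, followed by arithmetic for scale.

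**Step 1. Apply the rule to each case.**

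| Case | Start date on the record | Status under SAP 3.1.1 | Sensible? |
|---|---|---|---|
| A. New event on or after first dose | Post-dose | Treatment-emergent | Yes |
| B. Run-in event resolves, then returns on dosing | Post-dose, as a new episode | Treatment-emergent | Yes |
| C. Event open at first dose, never worsens | Pre-dose | Not treatment-emergent | Yes |
| D. Event open at first dose, worsens, site opens a separate record | Post-dose | Treatment-emergent | Yes |
| E. Event open at first dose, worsens, kept on one record | Pre-dose | Not treatment-emergent | No |

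Only case E is misclassified. Whether a participant falls in D or E depends on a site recording convention that the documents do not state.

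**Step 2. Find what case E is missing from.** It is absent from the treatment-emergent incidence and severity tables, the profile plots and the cumulative-incidence plots (SAP 6.2.1.3), and from the risk differences (SAP 3.1.1). It is not absent from the summaries of discontinuations, temporary discontinuations and dose reductions due to AEs (SAP 6.2.1.2 and 6.6.5), which are not limited to treatment-emergent events.

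**Step 3. Size per participant.** Inputs: 9 active and 3 placebo per cohort, 3 planned cohorts (protocol 4.1, SAP 2.3).

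- Active cohort: 1/9 = 11.1 percentage points.
- Placebo group of one cohort: 1/3 = 33.3 points.
- Placebo pooled over the three planned cohorts, if all enrol T2DM participants: 3 × 3 = 9, so 1/9 = 11.1 points.

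These shifts in incidence need a further condition: the participant has no other post-dose onset of the same preferred term during the treatment-emergent period. If there is one, the participant is already counted, and only the maximum severity may be understated.

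**Step 4. Frequency, by assumption only.** Let p be the chance that a given participant is a case E. The documents give no value for p. With independent participants, P(at least one among n) = 1 − (1 − p)^n.

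| Assumed p | 9 active participants | All 36 planned participants |
|---|---|---|
| 2% | 1 − 0.98^9 = 17% | 1 − 0.98^36 = 52% |
| 5% | 1 − 0.95^9 = 37% | 1 − 0.95^36 = 84% |
| 10% | 1 − 0.90^9 = 61% | 1 − 0.90^36 = 98% |

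The table shows how the answer depends on p. It is not an estimate.

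**The case against.** The strongest reply is that AE recording already handles the matter. Protocol 10.3.1 makes exacerbation of a pre-existing condition an AE in its own right, and the companion list of non-AEs exempts pre-existing conditions only if they do not get worse. A worsening entered that way carries a post-dose start date and passes the SAP rule. The detailed recording conventions belong to the CRF completion document named in protocol 10.1.5, which is not among the documents reviewed. This stands as a real route to correct classification. It does not close the gap, because no visible text tells the site to open a new record when the AE is already running. The follow-up text in protocol 10.3.3, which sends updated information to the documents first submitted, is generic and settles neither side.

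The scenario is also narrow, and that stands. The event must be open at first dose, worsen without first resolving, and stay on one record. Metformin must have been stable for at least two months before screening, and clinically significant gastrointestinal disease is excluded, so run-in symptoms may be uncommon.

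Three stronger readings are tempting and not supported:

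- A reader might infer that these events disappear from the safety reporting. They do not: AE-driven dose reductions and discontinuations are still summarised, and SAP 6.2.1.3 also reports AEs under sponsor standards that are not included here.
- A reader might infer that the rule systematically flatters the drug. It applies identically to both blinded arms.
- A reader might infer from the phrase active treatment in the second SAP sentence that placebo participants have no cut-off. The operative criterion refers simply to the first dose, and the sentence itself names Day 1. No participant would be classified differently.

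**Conclusion.** The gap is real and limited. As written, SAP 3.1.1 misclassifies an AE that is ongoing at first dose and then increases in severity, unless the site happens to enter the worsening as a new AE. The affected outputs are the treatment-emergent tables, the plots for nausea, vomiting and diarrhoea, and the risk differences.

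Neither the frequency nor the net direction can be derived from the documents. The active arm is understated only so far as the drug causes the worsening; placebo worsening is lost in the same way. For one affected participant, the effect is 11 points on an active cohort's incidence if there is no other post-dose onset of that term, and otherwise at most a severity grade. Safety is summarised descriptively and no hypothesis is tested, so no formal inference is at risk. The correction is still worth making, because gastrointestinal tolerability is what the study is meant to characterise and the change is small.

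**What to change.** In SAP 3.1.1, define a treatment-emergent AE as one that either

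- starts on or after the first dose of study intervention (PF-07081532 or placebo) and within the existing lag, or
- starts before that dose and increases in severity on or after it, within the same lag.

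State how the second group is identified: from a separate record dated at the worsening where one exists, and otherwise by reviewing all AEs ongoing at first dose before database release. Where the review finds a worsening, use its date as the onset for the plots and its grade for the severity table.

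Replacing active treatment with study intervention in the second sentence is an editorial tidy-up only.

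The cost is a short SAP amendment and a small review of AEs open at first dose, with possible site queries. SAP version 2 followed a data review ahead of database release, so a new instruction to close and reopen CRF records may come too late and would not be trivial; the review of ongoing AEs avoids depending on it. The documents do not show whether the CRF captures a severity change within one record. If it does not, the queries are the only source for those cases. No new visits or assessments are needed.
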